9.14 Significance level

There are no plans for any statistical inference. This study will adhere to the Guidelines for Good Pharmacoepidemiology Practices (GPP). Accordingly, data evaluations and interpretations will be based on point estimates and 95% confidence intervals (CI) for the evaluation of the statistical precision around the point estimate.

9.15 Software(s)

Analyses will be performed using SAS® Software version 9.4 or higher.

10 Study Participants

The subsections in this section describe the specifications for reporting participant disposition and study discontinuations.

10.1 Disposition of Participants and Discontinuations

Number of subjects screened (*full participant + data release participant*), number of subject enrolled (*full participant*), number of subjects in the SAF and in the DDI Safety Set will be presented by treatment group (never exposed to cladribine and exposed to cladribine) and total.

The number of subjects in the Lymphocyte Analysis Population will be summarized based on the SAF.

Study status will be summarized on the SAF by treatment group and total, presented as

- Completed or
- Discontinued.

Reason for study discontinuation will be summarized. Percentages will be presented with respect to the number of full participants.

Programming rule

Programming rule to cover potential unclean data: Patients who died will be set to study status "Discontinued", with reason ="Death".

Time since end of clinical trial, time since first dose will be summarized in weeks as a continuous variable and in cumulative intervals and in time intervals with the following categories:

Table 4 Time intervals

Cumulative intervals	Time intervals
Less than 12 weeks	1 to 84 days (12 weeks)
At least 12 weeks	85 to 168 days (24 weeks)
At least 24 weeks	169 to 252 days (36 weeks)
At least 36 weeks	253 to 336 days (48 weeks, 1y)
At least 48 weeks, 1y	337 to 420 days (60 weeks)
At least 60 weeks	421 to 504 days (72 weeks)
At least 72 weeks	505 to 588 days (84 weeks)
At least 84 weeks, 2y,	589 to 672 days (96 weeks, 2y)
At least 96 weeks, 3y,	673 to 1008 days (144 weeks, 3y)
Etc.	Etc.

Patient-year will be computed as the sum per group of the time since end of the clinical trial, in years. Patient-year will be presented per treatment group and total.

Reporting on study status will be done for SAF.

████████████████████
████████████████████

████████████████████
████████████████████

The disposition table will be repeated by

- CLARITY only
- CLARITY/CLARITY EXTENSION
- ORACLE MS
- ONWARD

10.2 Protocol Deviations

Important protocol deviations will be summarized by type of deviation. In addition, a listing of PREMIERE important protocol deviations will be provided.

Programming Note

Information will be taken from SDTM.DV dataset.

11 Demographics and Other Baseline Characteristics

Summaries will be presented on SAF by treatment group and total.

11.1 Demographics

The following variables will be presented. Variables with * are computed prior to first clinical trial study.

- Age at baseline (Registry Day 1), years and in categories (<= 40 y, >40 y)
- Sex (male, female)*
- Race*
- Region: America US, America non-US**, Western Europe, Australia, Eastern Europe, Russia, ROW*

**America non-US includes Canada and all countries from South America.

- Previous clinical trial: CLARITY only, ONWARD, CLARITY/CLARITY EXTENSION, ORACLE MS.
- Time since last Cladribine/Placebo dose (weeks)
- Total cumulative dose (mg/kg): summary statistics and in categories 0, >0-3.5, >3.5-5.25, >5.25-7.0, >7.0-8.75, >8.75.

11.2 Medical History

No reporting will be done.

12 Previous Medications or Medications/Procedures in PREMIERE

Medications in PREMIERE will be presented by Category, Therapeutic group (ATC level 2) and Preferred Name, per treatment group and total, using crude incidence:

Crude incidence, in % = (number of subjects with at least one medication / total number of subjects) * 100.

The following categories as reported in the CRF will be presented:

- MS-Related Immunomodulators and Immunosuppressants
programming note CM.CMSPID = 101-199
- MS-Related Symptomatic Medications, including pain control
programming note CM.CMSPID = 201-299
- MS-Related Antidepressants
programming note CM.CMSPID = 301-399
- OTHER MS- AND NON-MS-RELATED
programming note CM.CMSPID = 401-499

12.1 Previous medications

Reporting of previous medications was done previously in each initial study CSR. No reporting will be done for the PREMIERE CSR.

12.2 Medications in PREMIERE

Reporting will be done for SAF.

Medications in PREMIERE are medications (other than cladribine or placebo medications) which are taken by subjects at any time after (>) the end of clinical trial.

Data collection will be derived from PREMIERE dataset Concomitant Medication panel (SDTM.CM). Specifically, medications used during pregnancy collected for female partner of male patients will not be included (SDTM.CM CMCAT = “over the counter medications”, “prescription medications”).

12.2.1 Disease Modifying Drugs in PREMIERE

MS-disease modifying drugs (DMDs) drugs are defined by **custom selection** based on all concomitant medication collected.

Table 5 List of MS-DMD

Preferred Term (WHODD)
ALEMTUZUMAB
BETASERON /01229701/
DIMETHYL FUMARATE
FINGOLIMOD
FINGOLIMOD HYDROCHLORIDE
FUMARIC ACID
GLATIRAMER ACETATE
INTERFERON BETA
INTERFERON BETA-1A
INTERFERON BETA-1B
MITOXANTRONE
MITOXANTRONE HYDROCHLORIDE
NATALIZUMAB
PEGINTERFERON BETA-1A
RITUXIMAB
TERIFLUNOMIDE

Note: the final list of medications may be revised after database lock. Any changes from the list above will be described in the CSR.

12.3 Procedures in PREMIERE

Procedures are not coded in PREMIERE. No reporting will be done.

12.4 Handling of Partial dates for Medications

Missing and partial dates will be imputed considering the fact that medication may be considered as medication taken concomitantly to PREMIERE registry.

- Start missing day will be imputed to be 1 and start missing month will be imputed to be January.
- End missing day will be imputed to be the last day of the month. End missing month will be imputed to the last month of the year. In case of death, imputation rules will assure that no end dates are imputed after death.
- No imputation for complete start date and end date missing (day, month and year), and therefore medication will be ignored.

- If start date is completely missing (i.e. day, month, year missing) and end date is known or partially known then the start date will be imputed to be the Registry Day 1 minus one day if prior to end date, otherwise equal to end date.
- Complete end date missing (day, month and year) and partial or complete start date then will be imputed to be the last study assessment date.

13 Study intervention Compliance and Exposure

Not Applicable (please see section 7).

14 Efficacy Analyses

Not Applicable.

15 Safety Analyses

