#### **8.3.1.2 Information from medical health records review**

For subjects with lagged data period, Sponsor will review data from medical records and the PRP will enter the following data into the registry participant electronic case report form:

- Treatment exposure to immunosuppressant medications, including type of treatment, and date started;
- Occurrence of SAEs including time and outcome;
- Occurrence of a pregnancy in participant woman, including date of LMP, and outcome;
- In subjects tagged as “lymphopenic subjects” ascertainment of performance of a blood test during the lagged data period, and categorization of lymphocyte counts as normal, Grade 1 through Grade 4 or unknown, if available.

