## 8.4 Follow-Up Interviews

For MS subjects, the information to be ascertained in the follow-up interviews fall into five main categories:

- Updates in contact information
- Occurrence of SAEs (including time of event and outcome)
- Occurrence of AEs in the ‘Blood and Lymphatic System Disorders’ and ‘Neoplasms Benign, Malignant, and Unspecified’ SOCs (including time of event and outcome)
- Capture of any lymphocyte count assessments performed since last visit
- Prescription of immunosuppressant medications including type and start date

It is expected that subjects in PREMIERE will attend their routine MS care visits. The PRP is expected to request blood count and differential if lymphopenia has not resolved (i.e., lymphocyte count is equal or greater than  $0.8 \times 10^9/L$ ). All lymphocyte count results will be captured by the PRP regardless of monitoring frequency. Participating PRP will be instructed to have blood count and differential performed at least yearly until resolution of lymphopenia (i.e., a Grade 1 or Grade 0 lymphopenia), or end of the study period.

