Data collected from last value from the end of clinical trial to the last ALC value in PREMIERE will be presented and summarized on a continuous manner (absolute value only) and by grade, over time.

ALC Registry Baseline is defined as the first ALC date with a value on or after the end of clinical trial +1 day [Registry Day 1].

Programming rule to cover possible unclean data:

If first ALC date in PREMIERE is before the end of clinical trial, ALC Registry Baseline is defined as the first ALC value in PREMIERE on or after the end of clinical trial + 1 day.

A new set of time window are presented below using visit window computed relative to ALC Registry Baseline.

If more than 1 value is available for a particular time window for the same subject, the first value in the time window will be considered.

Table 8 Time window for lymphocyte from the end of clinical trial

Evaluation	Interval for analysis (day)
Last value from last clinical trial	
ALC Registry Baseline	First ALC date with value in PREMIERE registry
Week 12	[2 - 98]
Week 24	[99 - 182]
Week 36	[183 - 266]
Week 48, 1y	[267 - 350]
Week 60	[351 - 434]
Week 72	[435 - 518]
Week 84	[519 - 602]
Week 96, y2	[603 - 700]
Week 144, y3	[701 - 1036]
Etc.	[1037 - weekN*7+4*7]

Lymphopenia grade and MS-DMD

Best and Worst ALC grades will be presented in relation to use of MS-DMD medication. For subjects with MS-DMD medications reported at least once after end of clinical trial, the best and worst ALC grade will be selected on or after (\geq) the first MS-DMD.

The Worst and the Best grade will be summarized overall and by treatment group. Subjects who are not taking MS-DMD from the end of clinical trial +1 day to the end of PREMIERE will be excluded from the analysis.

Resolution of lymphopenia computed with observed ALC value

Subjects who complete or drop out at the end of the clinical trial with an unresolved lymphopenia will be presented, together with their outcome in PREMIERE registry. The outcome can be resolved or unresolved.

An unresolved lymphopenia is defined for a subject who left the end of a clinical trial without returning to normal or grade 1 ALC value after an episode of grade 3 or 4 lymphopenia. A grade 3 or 4 lymphopenia episode is defined by a start/end date. Start= ALC \geq grade 3, post baseline, End = following normal (grade 0) or grade 1.

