The duration (in months) of the resolved episodes (out of the unresolved at end of clinical trial period) will be summarized. In addition, use of MS-DMDs prior to resolution will be presented.

Resolution of lymphopenia computed using CRF tick box

Reporting will be done for SAF. This is an exception, to include the largest possible information available.

The number of subjects with declared Grade 3 or 4 lymphopenia at end of clinical trial [CRF Tick box], will be summarized together with their outcome in PREMIERE. The outcome in PREMIERE will be computed from those with at least one grade 0/1 in PREMIERE or with a CRF "resolution date".

Presentation per treatment group and total will be done.

Resolution of lymphopenia based on observed ALC value versus CRF tick box

A 2-by-2 table of number of subjects with and without resolution of lymphopenia at the end of clinical trial based on ALC value versus CRF Tick box will be presented.

In addition, a listing will be generated for subjects with unresolved lymphopenia at the end of clinical trial according to ALC grade, but with the CRF Tick box = "Resolved". The following variables will be displayed: Subject ID, cumulative dose of cladribine, previous clinical trial, treatment group (see section 9.1), all ALC values in PREMIERE with grade and date and tick box for resolved with date of resolved if available.

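### SAP 12.4 discards a PREMIERE medication record when both dates are missing, so a subject whose only MS-DMD record is undated is counted as without the drug

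*SAP*

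**What the plan says.** SAP 12.4 (Handling of Partial dates for Medications) rests on the premise that a "medication may be considered as medication taken concomitantly to PREMIERE registry". Its rules are:

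- Missing days or months are filled so as to give the widest interval, with end dates not allowed to pass death.
- "If start date is completely missing (i.e. day, month, year missing) and end date is known or partially known", the start is set to the day before Registry Day 1, or to the end date if that day does not precede it.
- "Complete end date missing (day, month and year) and partial or complete start date then will be imputed to be the last study assessment date".
- "No imputation for complete start date and end date missing (day, month and year), and therefore medication will be ignored".

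For immunosuppressants, the protocol names type and start date as the items to collect. Section 8.4 lists "Prescription of immunosuppressant medications including type and start date", and section 8.3.1.2 (lag-period record review) lists "Treatment exposure to immunosuppressant medications, including type of treatment, and date started". The lag questionnaire in 8.3.1.1 asks for the same two items. An end of treatment is listed only among the pregnancy items in 8.3.1.4.

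The medication data are used in three places. SAP section 12 reports crude incidence with all subjects as denominator. In SAP 15.1.4, the display of best and worst lymphocyte grade selects grades on or after the first MS-DMD, and "Subjects who are not taking MS-DMD from the end of clinical trial +1 day to the end of PREMIERE will be excluded from the analysis". The same section says that, alongside the duration of resolved lymphopenia, "use of MS-DMDs prior to resolution will be presented".

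**The concern.** A drug entered in the PREMIERE medication panel was reported by someone at a registry contact or for the lag period. Not knowing when it started is a gap in timing; it does not show that the drug was not taken. The rule nevertheless treats the record as if it did not exist, while the subject stays in the denominator.

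The pattern can plausibly occur. An ongoing drug has no stop date, and the protocol's item lists for immunosuppressants do not ask for one, so a completely unknown start date is then enough to lose the record. Lag-period information is retrospective. For a limited number of subjects without accessible records it comes from the subject directly (protocol 8.1, Subject Interviews), and recall of dates may be poor there.

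At stake is the description of other MS drugs used after cladribine. The most sensitive place is the lymphopenia display, where another drug taken before recovery is relevant context and the subset may be small.

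**Working it through.** **Inputs.** The date rules are from SAP 12.4, the crude-incidence formula from SAP section 12, and N = 1161 full participants from SAP section 7, Table 1. The share of MS-DMD users and the share of users known only from undated records are not in the documents; both are assumed below. The plan states no figure on this point, so there is none to reproduce.

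**Step 1: which records are lost.** Apply SAP 12.4 to each combination.

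| Start date | End complete | End partial | End missing |
|---|---|---|---|
| Complete | kept | kept | kept, end = last assessment |
| Partial | kept | kept | kept, end = last assessment |
| Missing | kept, start imputed | kept, start imputed | **ignored** |

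Eight of nine patterns are kept and one is dropped. If the end date is missing because the drug is ongoing, two of the three start-date states survive; a start year alone is enough.

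**Step 2: consistency with the rest of the SAP.**
- Within 12.4, an unknown start is tolerated if there is an end date, and an unknown end is tolerated if there is a start. Only the combination is treated as no record.
- SAP 15.6 gives an adverse event with a completely missing onset the earlier of Registry Day 1 and its resolution date, as a deliberate worst case. The undated event therefore stays in, while an undated drug is removed.
- SAP 9.13 keeps missing observations in the denominator and shows them as their own category. The medication rule provides no such category.

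**Step 3: where a subject with only undated MS-DMD records ends up.**
- Medication tables: in the denominator, not in the numerator.
- Lymphocyte grade in MS-DMD users: excluded.
- MS-DMD use before resolution: shown without one.

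**Step 4: illustrative size.** Let u be the true user share and f the share of users with only undated records. Then

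reported incidence = u × (1 − f).

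With N = 1161 and counts rounded to whole subjects:

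| u (true users) | f = 1% | f = 5% | f = 10% |
|---|---|---|---|
| 20% (232) | 19.8%, 2 lost | 18.9%, 12 lost | 18.0%, 23 lost |
| 40% (464) | 39.5%, 5 lost | 38.0%, 23 lost | 36.0%, 46 lost |
| 60% (697) | 59.4%, 7 lost | 57.0%, 35 lost | 54.0%, 70 lost |

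The loss runs from 2/1161 = 0.2 to 70/1161 = 6.0 percentage points. The Safety Analysis Population leaves out participants from the pantoprazole interaction study, so its N is at most 1161; the relative loss f does not depend on N.

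**The case against.** The strongest defence is that a record without any date cannot be placed in the analysis period. SAP 12.2 defines a medication in PREMIERE by its being taken after the end of the clinical trial, and it does not treat presence in the dataset as sufficient: partner pregnancy medications are also stored there and are removed. The best/worst grade display needs a first MS-DMD date that such a record cannot supply. Inventing both dates would sit badly with the no-imputation statements in protocol 9.3.1 and SAP 9.12. It could also place another drug before recovery from lymphopenia and so suggest an alternative explanation for a cladribine effect. This stands as an argument against imputing dates. It does not justify removing the record from a table that only asks whether a drug was used.

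The pattern may also be rare. The start date is an item the protocol collects, contacts are every three months for two years and yearly afterwards, incomplete data are queried (protocol 11.2), and any other usable MS-DMD record keeps the subject as a user. This also stands, and it limits the likely size.

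Three stronger inferences are tempting but not supported:

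- *Ongoing drugs are generally deleted because stop dates are not collected.* A missing end date alone never removes a record. SAP 12.4 also has rules for known and partial end dates, so the medication data evidently hold some.
- *Users are compared as if they were non-users.* The grade display excludes subjects without MS-DMD use, and the SAP contains no user versus non-user comparison.
- *Primary estimates are biased.* Medication dates do not enter the SADR or adverse-event incidences, and ALC-based resolution is defined from lymphocyte values and their dates.

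**Conclusion.** The point holds in limited form. The rule discards reported drug use, against the premise of its own section, and the SAP asks for no count of what was discarded. A reader of the report could not tell whether the loss was trivial.

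It affects descriptive outputs only: the medication tables and two MS-DMD displays within the lymphopenia section. Its size is unknown; the range of 0.2 to 6.0 percentage points rests wholly on assumed shares. The size of the unresolved-lymphopenia subset is not given either, so no figure can be put on that display. The conclusion also assumes that an undated entry in the registry panel usually reflects use after the trial, which is likely from how the data are gathered but cannot be shown for a single record.

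**What to change.** Replace the bullet in SAP 12.4 with wording such as:

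> If start and end dates are both completely missing for a subject's record in the PREMIERE medication panel (excluding partner pregnancy medications), no dates are imputed; the medication is counted as used in the medication tables and flagged 'date unknown'.

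In the two date-dependent displays of SAP 15.1.4 (grade on or after the first MS-DMD, and MS-DMD use before resolution), show subjects with only undated MS-DMD records in a separate row, 'MS-DMD used, date unknown'. Report the number of such records and subjects.

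The cost is a few lines of SAP text, one programming condition with a flag, and an extra row in two displays. The drawback is that a few drugs stopped before the end of the trial may be counted as registry use; the flag and the count make this visible.

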15.1 Primary Endpoints

15.1.1 Serious Adverse Events Related to Cladribine

Reporting will be done for SAF.

The objective is “to quantify and characterize the risk (cumulative incidence) of SADR, including malignancies and serious infections”.

Definition

The primary endpoint will be selected considering any serious adverse event characterized as Probable or Possible in the relationship to cladribine. Malignancies and serious infections will be considered in this endpoint only if the characteristics “serious” and “related” (“probable” or “possible”) are applicable.

Following protocol section 8.5.1.2, “an adverse drug reaction (ADR) is a response to a medicinal product which is noxious and unintended, and which occurs at doses normally used in man for prophylaxis, diagnosis, or therapy of disease or for the restoration, correction, or modification or physiological functions. Response in this context means that a causal relationship between a medicinal product and an adverse event is at least a reasonable possibility”.

The treating physician or other relevant concerned health care provider are asked to assess the relationship of the AEs to cladribine using the following definition, similar in all studies:

- Probable: A causal relationship is clinically/biologically highly plausible, and there is a correlation between the onset of the SAE and administration of cladribine, and between withdrawal of cladribine and resolution of the SAE.

- Possible: A causal relationship is clinically/biologically plausible and there is a correlation between the onset of the SAE and administration of cladribine.
- Unlikely: A causal relationship is improbable, and another documented cause of the SAE is most plausible.
- Unrelated: A causal relationship can be definitively excluded, and another documented cause of the SAE is most plausible.

The following statistics will be presented:

- Patient-year is the sum of the time since the end of clinical trial, expressed in years. Display with 1 decimal.
- m is the number of unique events. A unique event is a unique Preferred Term and date of onset per subject.
- n is the number of subjects with at least one event
- N is the total number of subjects in the treatment group
- AE (%) is the crude incidence. Display with 1 decimal.
 - $AE(\%) = (\text{number of subjects with at least one event} / \text{total number of subjects}) * 100$
- 95% Confidence Interval (CI) for the crude incidence within group for patients with at least one AE. The 95% Confidence Interval of the AE will be computed using the exact Clopper-Pearson confidence interval formula for binomial proportions (REF. Clopper item #3).

Statistics description

The following statistics per treatment group and total will be presented:

- Summary: Patient-years will be provided in the summary table. In addition, number of unique event, number of patients with at least one AE, crude incidence (%), 95% CI of the crude incidence. All these statistics will be repeated for AE leading to death and serious AE.

Note: SADR is a serious AE by definition. Therefore, only SADR and SADR leading to death will be presented.

- By SOC/ HLGT/ HLT/PT: Number of patients with the AE and crude incidence (%) will be presented by system organ class (SOC), High Level Group Term (HLGT), High Level Term (HLT), and preferred term (PT).

